which may have led to a floor effect, and the authors suggested that future studies consider only including participants who score above clinical cutoffs on psychopathology measures. Secondly, Kelly et al.'s (2009) self-soothing intervention comprised compassionate imagery, letter writing and self statements over only two weeks. It is possible that a multi-component compassion intervention cannot affect depression in so short a time, as participants have not had the chance to practise any of the techniques sufficiently. Thirdly, participant retention and adherence to the intervention were lower than expected in Hudson's (2015) study. The self-help booklet, while designed for people with skin conditions, focused on appearance-related distress and did not mention other common impacts of skin conditions, such as pain, itch, treatment burden and restriction of valued activities. Only 35% of participants agreed that they would recommend the self-help materials to a friend or family member, which indicates that there is scope to improve the materials themselves. In addition, one of the problems noted in the study was that some participants had trouble accessing the materials. This was resolved by putting the materials online, but this only happened towards the end of recruitment and so may have reduced participant engagement in the study.

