## **Acceptability and feasibility criteria**

Acceptability of intervention overall: The percentage of eligible participants who access the webpages will be calculated using Qualtrics data and user logins to the website. The intervention will be considered acceptable if at least 66% of eligible participants log into the website during their sixth week of the study. This criterion was chosen as a recent meta-analysis of computerised CBT for depression and anxiety disorders reported a median retention rate of 66% (Andrews et al., 2018).

Feasibility of providing online self-help: All eligible participants should be able to access the website, so if less than 90% of eligible participants log into the website during their first week of the study, this may suggest that there were problems with accessing the self-help website. This criterion was chosen as more than one in ten people having

difficulty accessing the website is analogous to experiencing a ‘very common’ side effect of a medication (NHS, 2018). User logins for subsequent weeks of the intervention will also be recorded.

Feasibility of providing guidance: Researcher time spent providing email guidance will be recorded, and will be considered feasible if this takes 120 minutes or less per patient over the study period. This criterion is derived from guidance on individual guided self-help interventions for people with depression, which typically consist of up to 240 minutes overall (up to eight sessions at 30 minutes each; NICE, 2010; National IAPT Programme, n.d.): if providing email guidance takes over half the amount of time needed for individual guided self-help programmes, then it cannot reasonably be argued to be “limited facilitation” (NICE, 2010, p. 23). The percentage of participants who requested additional support via email will also be recorded. These figures will inform future trials and implementation of guided self-help for people with skin conditions within health services.

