week after completing the baseline measures participants will receive an automated email inviting them to access the second session of the intervention. Automated emails will continue to be sent in this way, with homework reminders and links to subsequent sessions. The emails will also invite the participant to contact the researcher if they require further support with the self-help materials. The researcher will respond to any such emails individually. One week after the last session participants will be invited to provide feedback via Qualtrics about the guided self-help intervention overall, and to complete the outcome measures again.

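### The week-1 login criterion is justified by access difficulty but counts non-login for any reason, so a result below 90% cannot separate people who could not get in from people who chose not to start

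*Combined protocol and SAP*

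**What the plan says.** In Acceptability and feasibility criteria, the paragraph on providing online self-help begins with ability: "All eligible participants should be able to access the website". What it measures is behaviour, since the trigger is "if less than 90% of eligible participants log into the website during their first week of the study". The inference drawn from that is tentative: "this may suggest that there were problems with accessing the self-help website". The cut-off of one in ten is borrowed from the frequency of a very common drug side effect, on the ground that "difficulty accessing the website is analogous to experiencing a" reaction of that kind.

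The preceding paragraph uses the same measure, five weeks later, for a different property: "The intervention will be considered acceptable if at least 66% of eligible participants log into the website during their sixth week of the study". Under Ethical issues (Confidentiality), login tracking is described as a way to monitor engagement.

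Other places that bear on the point:

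- **Procedure.** The day-3 reminder is worded to cover people who have not yet done session 1. Session-1 feedback is requested at the end of that session. The automated emails "invite the participant to contact the researcher if they require further support". The final survey invitation has no stated login condition.
- **Measures.** Weekly feedback includes webpage usability ratings and open comments. The final feedback has open questions on what was unhelpful and what could be improved.
- **Acceptability and feasibility criteria.** Logins in later weeks and the percentage of participants asking for email support are also recorded.

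**The concern.** The reason given for 90% holds only if each week-1 non-login is an access difficulty. The plan itself treats logins as engagement elsewhere and expects that some people will not have started by day 3. The count can therefore mislead in both directions: a person who loses interest adds to the signal, while a person who struggles and gets in on day 6 does not.

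The feasibility of providing the self-help online is a stated aim. The background section on compassion self-help for skin conditions reports that in an earlier study "some participants had trouble accessing the materials", and The Current Study lists hard-to-access materials among the limitations it sets out to address. If the login rate falls below 90%, the team needs to know whether to repair the login process or the uptake strategy. If it does not fall below 90%, the team still needs to know how many had trouble before getting in. The login rate alone answers neither question.

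**Working it through.** **Inputs from the documents**

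- Threshold (Acceptability and feasibility criteria): fewer than 90% logging in, from more than one in ten with difficulty: 1 − 0.10 = 0.90.
- Smallest recruited sample (Sample size): 12 / (1 − 0.48) = 23.08. The plan gives 23, which reproduces to the nearest whole number.
- Largest sample (Sample size): 9 × 60 / 10 = 54. Reproduces.

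**Assumed input**

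- q, the chance that a participant who could get in does not log in during week 1. The documents give no figure, so a range of 5% to 20% is shown.

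**Step 1: how many non-logins take the rate below 90%**

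- n = 23: 21/23 = 91.3% and 20/23 = 87.0%, so 3 or more.
- n = 54: 49/54 = 90.7% and 48/54 = 88.9%, so 6 or more.

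**Step 2: chance of this with no access failure**

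The number of non-starters X is binomial (n, q). The chance is P(X ≥ 3) at n = 23 and P(X ≥ 6) at n = 54. For n = 23 and q = 0.10:

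1 − [0.9^23 + 23 × 0.1 × 0.9^22 + 253 × 0.01 × 0.9^21] = 1 − [0.0886 + 0.2265 + 0.2768] = 0.408.

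| Assumed non-start rate | n = 23 | n = 54 |
|---|---|---|
| 5% | 10.5% | 5.2% |
| 10% | 40.8% | 45.7% |
| 15% | 69.2% | 84.0% |
| 20% | 86.7% | 97.2% |

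**Step 3: can the rule tell the causes apart?**

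Let a be the proportion unable to get in. The login probability is (1 − a)(1 − q), which is symmetric in a and q.

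- a = 15%, q = 0: login probability 0.85; below 90% in 69.2% (n = 23) and 84.0% (n = 54) of studies.
- a = 0, q = 15%: login probability 0.85; the same 69.2% and 84.0%.

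The symmetry does not depend on which rates are assumed.

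**Step 4: do other planned data separate them?**

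- Session-1 feedback comes at the end of that session, so it comes from people who got in.
- Support requests are to be recorded as a percentage, with no reason specified.
- Later-week logins show late entry but not why it was late.
- Open final feedback may reach non-starters, but the main text describes no question to them about access.

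The start of the first week is also not defined. Automated emails are timed from baseline completion, whereas login details go out only after the researcher registers the participant. Registration delay is thus a further possible cause of non-login.

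**The case against.** The strongest reply is that the plan never declares an access failure. The other two criteria in that section use verdict wording; this one says only "this may suggest that there were problems with accessing the self-help website". That stands. A reader might infer that early disengagement will be reported as a technical fault, or that the feasibility question goes unanswered. The hedge does not support either reading. It does admit an ambiguity that the plan then gives no means to resolve.

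A reader might also infer that the 90% rule is the only information on access. It is not: support-request percentages, later logins, usability ratings and open feedback all bear on it, and someone who got in late after a struggle can say so in the session-1 feedback. Nor can one state that no question on access exists, because the item lists in Appendices I and J are not in the text available for review. The supportable statement is that the main text describes none for non-loggers.

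The earlier study's access problem was, by the plan's account, resolved by moving the materials online, and this study is online from the start. That lowers the stakes without removing the question.

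On size, the 41% and 46% arise when true non-login sits exactly on the threshold, where a cut-off of this kind is crossed somewhat under half the time. At 5% non-start the figures are only 11% and 5%. It is tempting to cite the 48% in Sample size as support for high non-start, but that is overall attrition at the 75th percentile of internet-based CBT studies, not first-week non-start.

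Finally, replacing logins with volunteered reports would exchange an objective measure, available for every eligible participant, for one that is missing in dropouts. That objection is sound, and the fix below keeps the login rate.

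**Conclusion.** The point holds as a gap in interpretation, not as an error in a figure. The criterion's justification concerns difficulty, its count concerns non-login from any cause, and nothing described in the main text connects the two. With no access failure, 3 of 23 or 6 of 54 non-starters suffice to go below 90%. How often that would happen depends wholly on the assumed non-start rate and on participants behaving independently; the inability to separate the causes depends on neither. The change is a cheap improvement that would let the study answer its own feasibility aim. It should be in place before recruitment, since reasons for not logging in are hard to recover afterwards.

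**What to change.** Keep the 90% week-1 login rate as an objective screening indicator, and state that it will not be read on its own as an access problem. Then:

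1. Add a yes/no item on difficulty getting into the website to the end-of-study Qualtrics survey, and send it to all participants, including those who never logged in.
2. Add one line to the existing day-3 and day-7 emails asking anyone who could not log in to say so.
3. Tally access-related emails and bounced login emails separately from other support requests.
4. Report week-1 non-logins as access failure, non-uptake or unknown. Compare access difficulty with the 10% threshold, counting unknowns first as no difficulty and then as difficulty.

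As an illustration, suppose 3 of 23 do not log in: one reports being unable to, one reports choosing not to start, one is silent, and nobody who logged in reports difficulty. The login rate is 20/23 = 87.0%, below the cut-off. Access difficulty lies between 1/23 = 4.3% and 2/23 = 8.7%, under 10% either way. If all three are silent, the range is 0/23 = 0% to 3/23 = 13.0%, and the result is openly inconclusive.

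The cost is one survey item, one line in two emails and a tally. The small downside is that silent non-users stay unclassified, so the range will be wide if most non-loggers do not reply.

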## Method

### Design

Given that the current study aims to investigate a novel intervention, the study will be an acceptability and feasibility study that uses a pre–post design.

### Participants

Participants will be adults who are currently living with a skin condition and who are experiencing symptoms of depression, as identified by scoring 10–20 on the depression subscale of the Depression Anxiety Stress Scales (DASS; Lovibond & Lovibond, 1995), which represents mild–moderate levels of depressive symptomatology. The stepped care model expects that people with mild–moderate depression will benefit from guided self-help (NICE, 2009), whereas people with more severe depression may require more intensive interventions. Participants will be recruited online, in line with the format of the intervention. The following skin charities/organisations have already agreed to advertise the study on their websites and/or their social media channels when ethical approval has been granted:

- British Skin Foundation
- British Association of Dermatologists
- DEBRA (epidermolysis bullosa)
- Lupus UK
- National Eczema Society
- Pem Friends (pemphigus and pemphigoid)
- Psoriasis Association

If it is necessary to recruit more participants after skin condition organisations have advertised the study, email advertisements will be sent to an existing volunteer list from a previous study ([name], [name], & [name], 2019), to members of the University of Sheffield's volunteers lists, and to students at Sheffield Hallam University's Psychology department. Snowball sampling will be used, where potential participants will be asked to forward the study advert to family and friends who might be interested in participating.

### **Inclusion criteria**

- Self-reported as currently experiencing a skin condition that has been diagnosed by a medical professional.
- Scored between 10 and 20 (inclusive) on the depression scale of the DASS at baseline.
- Age 18 or over.
- Sufficient English language ability to read self-help materials and complete self-report questionnaires.

### **Exclusion criteria**

- Currently having psychological treatment for a mental health condition.

- Diagnosis of a serious mental illness (e.g. bipolar disorder or psychosis).
- Diagnosis of a drug/alcohol addiction.

## Procedure

Data will be collected using Qualtrics, an online survey provider. In the study advert, participants will be provided with a link to the Qualtrics survey page, where they will read the participant information sheet and complete an online consent form (see Appendices A and B). Screening questions relating to the exclusion criteria will be asked before participants complete the demographic questions, clinical information, and baseline measures (see Appendices C–H). Baseline DASS depression scores will be calculated automatically by Qualtrics. Any participants who disagree with the consent statement or who are ineligible for the study will be re-directed to an ‘end of study’ webpage. This will explain that they are not able to continue with the study and recommend that they contact their GP if they need further support. Signposting information about mental health resources and emotional support for skin conditions will also be provided to all participants.

Qualtrics will notify the lead researcher when an eligible participant has completed the baseline survey. Eligible participants will be registered as users on the study website by the researcher and then sent an email with their login details and a link to the study website, with instructions to access the first session of the intervention. Anyone that attempts to access the intervention webpages without logging in will be redirected to the login page—the only exceptions to this are the homepage and the contact page. Requiring participants to log in means that engagement with the intervention can be monitored without involving any third parties for website traffic statistics (for example, Google Analytics), and also means that each participant’s use of the website can be accurately tracked no matter what devices they use. At the end of the first session, participants will be asked to provide feedback on the first session, which will be collected using Qualtrics. Participants will receive an automated email three days after completing the baseline measures to remind them to practise the homework exercise (or go through the session if they haven’t already done so). One

week after completing the baseline measures participants will receive an automated email inviting them to access the second session of the intervention. Automated emails will continue to be sent in this way, with homework reminders and links to subsequent sessions. The emails will also invite the participant to contact the researcher if they require further support with the self-help materials. The researcher will respond to any such emails individually. One week after the last session participants will be invited to provide feedback via Qualtrics about the guided self-help intervention overall, and to complete the outcome measures again.

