participants advise the researcher of any adverse effects via email, the researcher will be able to re-iterate options for further support as appropriate. The researcher previously worked in primary care mental health services for five years, providing guided self-help to people with depression and anxiety disorders, and is therefore experienced in dealing with emotional distress and signposting appropriately. If necessary, the researcher will discuss concerns with her primary supervisor, who is a clinical psychologist.

**Confidentiality.** Participants will be informed that their data will be kept confidential and that they will not be personally identifiable in any results of the study. Unique identification numbers will be used throughout the data sets. A data file will be created to contain participants' details and their identification numbers, for matching up quantitative data over time and to allow the destruction of data should participants wish to withdraw from the study. This data file will be password-protected and kept separately from the rest of the participants' data.

Spreadsheets containing participants' names and email addresses will also be created in order to administer the study—for sending emails on the correct dates and tracking participants' logins. No sensitive quantitative data will be kept in these spreadsheets, only dates. These spreadsheets will also be password-protected and kept separately from outcome measures and feedback data. Once data collection is complete, participants' names and email addresses will be replaced with their unique identification numbers.

Participants will be required to log into the study website solely to track user logins for the purpose of monitoring participants' engagement with the intervention from week to week. Participants will log into the website with a username (usually their first name) and password that has been allocated to them by the researcher.

Participants will not be asked to provide any data via the study website, nor will they be able to access any other participants' details. No-one except the researchers involved in the study will have access to participants' contact details.

**Data protection.** Personally identifiable digital data will be stored securely as described above, on the lead researcher's university filestore. The lead researcher will be

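### The 66% acceptability rule counts week-6 logins only, and the plan does not say that a signed-in participant's visit is recorded, so use may be undercounted

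*Combined protocol and SAP*

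**What the plan says.** Under Acceptability and feasibility criteria, the intervention counts as acceptable "if at least 66% of eligible participants log into the website during their sixth week of the study". The threshold is a benchmark: the median retention rate from a cited meta-analysis. The same paragraph opens with a broader statement of sources: "The percentage of eligible participants who access the webpages will be calculated using Qualtrics data and user logins to the website". It does not say how the two sources are combined, and the sentence that sets the rule mentions logins alone.

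The Procedure section describes the access control: "Anyone that attempts to access the intervention webpages without logging in will be redirected to the login page". Only the homepage and the contact page are exempt. It concludes that each participant's "use of the website can be accurately tracked no matter what devices they use". On reaching later sessions it says: "Automated emails will continue to be sent in this way, with homework reminders and links to subsequent sessions".

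Under Ethical issues (Confidentiality), the stated purpose is narrower: "Participants will be required to log into the study website solely to track user logins", so that engagement can be followed from week to week.

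Under Measures, participants are asked for feedback on every weekly session. The Procedure section says that the session 1 feedback is collected in Qualtrics.

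**The concern.** A login shows that a visit began with a password. It captures every visit only if every visit requires one. As written, the redirect meets people who are not logged in, and the sessions are reached from links in emails. If a sign-in from an earlier week were still live, a participant could open session 6 without producing a login in week 6. The plan states no sign-in duration, no sign-out between sessions and no record of pages opened by a signed-in user. Its claim of accurate tracking therefore has no stated mechanism behind it.

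At stake is the only numerical pass mark for acceptability. A missed login can only lower the recorded figure, never raise it. The weekly login figures after week 1 are open to the same error. The 90% first-week access criterion is much less exposed, because a participant's first access needs a login.

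**Working it through.** **Denominators (Sample size section).** The plan recruits 23 so that 12 remain after 48% attrition: 12 / (1 − 0.48) = 23.08. This rounds up to 24, but 23 × 0.52 = 11.96, so the stated 23 is reproduced to within one participant. The maximum is 9 × 60 / 10 = 54, as stated.

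**Pass marks.**
- N = 23: 0.66 × 23 = 15.18, so 16 are needed (16/23 = 69.6%; 15/23 = 65.2% fails).
- N = 54: 0.66 × 54 = 35.64, so 36 are needed (36/54 = 66.7%; 35/54 = 64.8% fails).

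**Assumed quantities.** Let p be the true share of eligible participants who use the site in week 6, and m the share of those users with no login on any day of that week. The documents give neither, so both are shown over a range. The expected recorded rate is p(1 − m).

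**Break-even.** Setting p(1 − m) = 0.66 gives m = 1 − 0.66/p.

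| True use p | Missed share m that brings the expected recorded rate to 66% |
|---|---|
| 70% | 1 − 0.66/0.70 = 5.7% |
| 75% | 1 − 0.66/0.75 = 12.0% |
| 80% | 1 − 0.66/0.80 = 17.5% |
| 85% | 1 − 0.66/0.85 = 22.4% |
| 90% | 1 − 0.66/0.90 = 26.7% |

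**Chance of passing.** This is P(X ≥ pass mark), with X binomial (N, p(1 − m)).

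| p | m | N = 23 (need 16) | N = 54 (need 36) |
|---|---|---|---|
| 75% | 0 | 0.804 | 0.938 |
| 75% | 5% | 0.668 | 0.816 |
| 75% | 10% | 0.515 | 0.615 |
| 75% | 20% | 0.237 | 0.195 |
| 80% | 0 | 0.928 | 0.993 |
| 80% | 10% | 0.697 | 0.847 |
| 80% | 20% | 0.375 | 0.400 |

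The m = 0 rows apply if every visit forces a login, or if all use is counted by other means. Near the threshold a small undercount matters. At true use of 85% to 90%, more than a fifth of active users would have to be missed before the expected rate fell to 66%.

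**The case against.** The strongest reply is that the mechanism is assumed. Nothing in the documents says that a sign-in outlasts a visit, and the redirect sentence describes access control, not session length. The condition is also narrow. An active user is missed only if the sign-in dates from before week 6 and covers every visit in that week. One visit after sign-out, or from a device that is not signed in, produces a login and the person is counted. All of this stands, and it is why the point is conditional.

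The plan also names Qualtrics data as a source, and a signed-in user who gives session 6 feedback would leave a record there. This stands in part. The rule itself uses logins only, no method of combining the sources is given, and a user who skips the feedback would still not be seen. Nor is the login rule the only evidence on acceptability: the Aims include explicit feedback, and the Measures add open questions and an adapted Friends and Family Test. It is, however, the only part with a numerical pass mark.

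A reader might infer more: that recorded retention is biased downward, that the weekly figures will show a false decline, or that the loss falls mainly on the most engaged participants. The documents support none of these. Each depends on an unstated website setting, and nothing shows that an undercount would grow from week 2 to week 6. A reader might also take the statement that the administrative spreadsheets hold only dates as proof that the site records nothing else. That statement concerns confidentiality and does not describe everything the site logs.

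**Conclusion.** The point holds as a possible undercount, not a demonstrated one. The 66% rule uses login as a proxy for use. The plan does not state the conditions under which the two agree, and any disagreement runs in one direction, towards a false finding of not acceptable. The actual size cannot be derived from the documents and may be zero. Under the assumptions shown, with true week-6 use of 75% and 10% of active users missed, the chance of passing would fall from 0.804 to 0.515 with 23 participants, and from 0.938 to 0.615 with 54. It is worth settling before recruitment, because visits that were never recorded may not be recoverable afterwards.

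**What to change.** Before recruitment, define a participant as active in a study week if at least one of these exists for that week: a login, a recorded intervention-page access by that user, or feedback on that week's session submitted in Qualtrics during that week. Apply the 66% rule, with its threshold unchanged, and the weekly figures to that count. Alternatively, set the site to end sign-ins between weekly sessions and say so in the plan.

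Then reconcile the text:
- In Acceptability and feasibility criteria, state how Qualtrics data and logins combine, and align the 66% sentence with it.
- In Procedure, bring the accurate-tracking sentence into line with the mechanism chosen.
- If page access is logged, amend the statement under Ethical issues that login serves only to track logins, and check the participant information for the same point.

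The cost is a minor website change plus wording. The feedback is already being collected. Forced sign-out means an extra password entry for participants, which could itself discourage some visits. Counting any evidence of use avoids that.
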